Aim 1: Discover Phase (3 months). Using iterative and participatory methods, we will interview up to 15 clinicians from FHQCs affiliated with the WWAMI region Practice Research Network (WPRN, a collaborative group of primary care practices through the states of Washington, Wyoming, Alaska, Montana and Idaho to facilitate innovative community-based research), and observe them in routine practice to identify usability challenges. Contribution to the Center: Data from this phase will be used to inform the Typology of EBPI Targets.

Aim 2: Design/Build Phase (6 months) After identification of potential targets, the research team will work via Zoom teleconferencing with the original clinicians from the discover phase and 0-5 new clinicians to engage in a rapid cycle of iterative prototype development and testing (e.g., storyboarding, paper prototypes) of BA modifications. The build of these modifications will include the development of intervention prototypes for user testing and refinement with input from these care managers. Contribution to the Center: Data from this phase will be used to inform the Matrix of EBPI Modifications.

Aim 3: Test Phase (15 months). We will test and compare the BA modification (modBA) to usual care in a small non-randomized trial. We will assign all provider teams (therapist & care manager(s)) in the clinic to use modBA with 10 patients per team for a total of 40 patients. We will then compare patient outcomes for those receiving modBA vs. 40 patients receiving usual clinic care. **H1:** Modifications developed in the Design/Build phase for targets identified in the Discover Phase will result in better usability (System Usability and User Burden Scales) compared to usual care.

H2: modBA will be more effective than usual care on improving clinical outcomes of functional disability (Sheehan Disability Scale [SDS]), change in depression symptoms over time (PHQ-9 total score), and change in anxiety symptoms over time (GAD-7 total score).

1.6 Study design. Provide a one-sentence description of the general study design and/or type of methodology.

Your answer will help HSD in assigning applications to reviewers and in managing workload. Examples: a longitudinal observational study; a double-blind, placebo-controlled randomized study; ethnographic interviews; web scraping from a convenience sample of blogs; medical record review; coordinating center for a multi-site study.

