2 PARTICIPANTS

2.1 Participants. Describe the general characteristics of the subject populations or groups, including age range, gender, health status, and any other relevant characteristics.

Discover and Design/Build Phases: We will recruit up to 15 behavioral health clinicians and care managers from the partnering FQHC. For the Test Phase, we will recruit up to 11 clinicians and care managers and 80 patient participants. Patient participants must be 18 years or older and suffering from mild to moderate depression.

2.2 Inclusion and exclusion criteria.

a. Inclusion criteria. Describe the specific criteria you will use to decide who will be included in your study from among interested or potential subjects. Define any technical terms in lay language.

- Clinicians – must deliver behavioral treatment as part of standard clinical workflow and work at the partnering FQHC
- Participants – 18 years or older suffering from mild to moderate unipolar depression as measured by PHQ-9 score between 10-20, and the capacity to provide written consent for research assessment. (Phases 2 and 3)

b. Exclusion criteria. Describe the specific criteria you will use to decide who will be excluded from your study from subjects who meet the inclusion criteria listed above. Define any technical terms in lay language.

Clinicians who do not speak English are excluded from all phases of the study. Patient participants in Phases 2 and 3 who have 1) Intent or plan to attempt suicide in the near future; 2) history or presence of psychiatric diagnoses other than unipolar, non-psychotic major depression or generalized anxiety disorder will be excluded.

2.3 Prisoners. IRB approval is required in order to include prisoners in research, even when prisoners are not an intended target population.

a. Will you recruit or obtain data from individuals that you know to be prisoners?

For records reviews: if the records do not indicate prisoner status and prisoners are not a target population, select “No”. See the [WORKSHEET: Prisoners](#) for the definition of “prisoner”.

No

Yes → If yes, answer the following questions (i – iv).

i. Describe the type of prisoners, and which prisons/jails:

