Participants must be 18 years old or older, suffering from mild to moderate depression. The site champion will identify potential participants from their electronic health records (EHRs) who score between 10 and 20 on the PHQ-9. Patient procedures include:

- Up to 40 patients who are already receiving care at BVHC will receive care via the BA task-sharing model
- We will also include a sample of up to 40 other patients who are already receiving care at BVHC (but not yet receiving care via the modified BA model) who will continue to receive their usual care
- Patients will complete weekly PHQ and GAD (already being collected by BVHC as part of usual care). This includes both the patients who are receiving care via the BA task-sharing model and those who are receiving care without the model
- We will collect historic patient data (PHQ and GAD, already collected by BVHC and agreed to by patients) for all patient participants. This includes both the patients who are receiving care via the BA task-sharing model and those who are receiving care without the model.
- We will collect 3-month follow up patient data (PHQ and GAD, already collected by BVHC and agreed to by patients) for all patient participants. This includes both the patients who are receiving care via the BA task-sharing model and those who are receiving care without the model.
- We will ask up to 10 patients who received care via the BA task-sharing model to complete exit interviews to give their perspective on the care they received. Patients will be consented for these

interviews, as we will then be asking patients to complete research activities that are beyond activities already completed during their usual care. Patients will be paid \$25 for the exit interviews.

- 5.2 Data variables.** Describe the specific data you will obtain (including a description of the most sensitive items). If you would prefer, you may upload a list of the data variables to the **Supporting Documents** SmartForm instead of describing the variables below.

Clinician Data:

Phase 1 & 2 qualitative clinician interviews:

We request flexibility in qualitative interviewing questions with clinicians during Phase 1 and 2 which will include:

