- common problems clinicians experience or anticipate in **usability** of EBPIs such as: (1) too many steps in a typical session; (2) not enough time to “get to know” the patient/not enough time to get through the process of EBPI in each session; (3) too tiring to deliver on days when clinicians see patients back to back; (4) focusing on problems was not synergistic with clinic mandates to use strength-based interventions; (5) difficulty using EBPIs to address common problems, such as lack of motivation, affect regulation, profound pessimism, trauma exposure, and access to basic needs in the face of poverty (food, shelter, access to health care, safety); (6) insufficient support to know when adding other EBPI elements or eliminating EBPI elements was appropriate or in violation of protocol; and, (7) over insistence by trainers or supervisors to have clinicians structure sessions and use of forms.
- Implementation domains to include (1) intervention characteristics, including core components and adaptable, peripheral elements; (2) outer setting, the broader economic, political, social context in which an organization exists; (3) inner setting, the immediate organizational context in which implementation occurs, including shared receptivity to change; (4) individual characteristics of practitioners and implementation team members, such as personal and professional values, interests, and affiliations; and (5) the implementation process, the steps and modes by which active change is undertaken.
- Questions about what clinicians value about their work with their patients, what they feel is missing when using EBPIs, and suggestions for how it could be improved, given their clinical context and patient population.

Phase 3

Clinician Participants:

Clinician Training:

Adherence Scale (checklist) – to be developed in Phase 2

Intervention Usability:

- AIM (already uploaded to Zipline in “Assessments” pdf)
- IAM(already uploaded to Zipline in “Assessments” pdf)
- FIM (already uploaded to Zipline in “Assessments” pdf)
- User Burden Scale
- System Usability Scale
- Qualitative adherence questions
- Qualitative adherence/modification questions (at 3-month follow up)

Demographic Survey

Patient Participants:

- Demographic info (EHR)
- Process measures (eg. how long have patients been in treatment, how frequently do they have visits, etc.) – (EHR)
- 9-Item Patient Health Questionnaire (PHQ-9) – (EHR)
- 7-Item Generalized Anxiety Disorder (GAD-7) – (EHR)

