A final prototype will undergo initial feasibility evaluation in pilot field deployments with each clinician using the prototype with one patient. Once we have completed the redesign of BA so that it (1) meets needs of its clinicians and patients (i.e., is useful), and (2) is easy to use and understand (i.e., is usable), we will move to the *Test* phase of this study.

Phase 3/Aim 3: Test phase (15 months). We will conduct a pilot study comparing the modified version of BA to usual care. Therapists will be randomized to either modified BA, and will use their assigned intervention with 5 patients.

Patient eligibility. Patient participants will be identified through each clinic's electronic health record. Participants must be 18 years old or older, suffering from mild to moderate depression. The site champion will identify potential participants from their electronic health records (EHRs) who score between 10 and 20 on the PHQ-9 and will contact potentially eligible patients to conduct a preliminary screening for eligibility, provide a brief description of the study and obtain informed consent.

Clinician training in modified BA. [name] and [name] will train clinicians in the modified BA. We will follow the protocol developed by the AIMS Center, which includes training in basic brief treatment skills, therapeutic elements of the intervention and therapy process. This is followed by simulated case training.

Clinician data collection. Two types of data will be collected, clinician assessment of intervention usability, and clinician ability to learn the intervention and maintain competency. To measure **intervention usability**, clinicians will complete the ALFA-Q Acceptability Scale, the User Burden Scale and the System Usability Scale, which are core measures for this Center (see **Methods Core** for description of scales). **Learnability** of the interventions will be measured in number of role plays needed to reach competency during training. To measure **sustained competency**, clinicians will collect audio recordings of patient sessions for review by experts. Drs. [name] and [name] will conduct these reviews using each intervention's adherence scale. Sustained competency will be defined by (1) time to first session rated < 4 ("good") and (2) number of sessions rated < 4 ("good") once certified. Clinicians will not be given feedback on session performance.

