Patient data collection. We will use the UWAC data portal, which will be based on the UWAC Data portal⁸⁴ designed specifically for research on mobile depression interventions to confirm eligibility, complete the consent process, and conduct baseline and outcomes assessment (see **Methods Core** for further details.) For qualitative interviews, we will use Zoom.com, a secure teleconferencing service with HIPAA-compliant data security features and the capacity to record sessions. Patients can participate either by phone or video. Participants will receive \$20 for completing each of 2 (baseline and post-treatment) assessments. Patient data will be collected before treatment initiation and after treatment ends. Patients will complete a demographic survey to determine gender, age, race/ethnicity, income categories, and educational level. Patients will complete a series of brief clinical measures to determine the presence of a depressive disorder and if there are any important comorbidities. The *Sheehan Disability Scale (SDS)*^{85,86} is a brief analog scale measuring functioning in work, social, and health domains, using visual-spatial, numeric and verbal anchors. The scale has been validated in medical and psychiatric populations with a variety of psychiatric diagnoses.^{85,86} The *9-item Patient Health Questionnaire*⁸⁷ (PHQ-9) consists of 9 DSM depression symptoms and one disability item. It has been found to have excellent sensitivity to change over time (sensitivity = .88, sensitivity = .80).⁸⁸

Data analysis. Aim 3 focuses on pilot feasibility data to inform a larger (future) clinical trial comparing modified BA to usual care. Thus, analyses do not focus on hypothesis-driven inferential statistics but rather on descriptive statistics, graphical summaries, and basic effect sizes. **H1: Usability.** Differences in clinician-reported usability

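### Stage of treatment is uncontrolled in the non-randomized PHQ-9 and GAD-7 comparison: there is no common index visit or baseline rule, and the time-in-treatment data collected have no role in the analysis

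*Combined protocol and SAP*

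**What the plan says.** **Design.** Aim 3 in section 1.5 states: "We will test and compare the BA modification (modBA) to usual care in a small non-randomized trial". The patient hypothesis there (H2) concerns, besides functional disability, "change in depression symptoms over time (PHQ-9 total score), and change in anxiety symptoms over time (GAD-7 total score".

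**Who enters.** Section 5.1, Patient Procedures, gives the modBA group as "Up to 40 patients who are already receiving care at BVHC will receive care via the BA task-sharing model", and the comparator as a "sample of up to 40 other patients who are already receiving care at BVHC (but not yet receiving care via the modified BA model". Section 2.2 describes patients as "suffering from mild to moderate unipolar depression as measured by PHQ-9 score between 10-20" and adds exclusions for suicidal intent and for other psychiatric diagnoses. No criterion concerns a new episode, sessions already received or time in treatment.

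**What is collected.** For both groups, section 5.1 lists historic PHQ and GAD scores, weekly scores and 3-month follow-up scores. Section 5.2 adds process measures from the EHR, for example "how long have patients been in treatment, how frequently do they have visits"; section 5.7 repeats them.

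**How it is analysed.** The Data analysis paragraph of the attached research plan, which labels patient outcomes H3, specifies plots, means and SDs, Cohen's d and a t-test between treatments. It names no covariate and gives no use for the historic scores or for time in treatment.

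**Baseline.** The only timing rule is in the attached plan under Patient data collection: "Patient data will be collected before treatment initiation and after treatment ends".

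**The concern.** A change score needs a start point, and none is fixed. A modBA patient could be counted from the first modBA visit. A usual-care patient has no such event, so the person drawing the charts must choose a date.

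The entry rule also admits patients with different expected courses. Someone newly referred with a PHQ-9 of 15 and someone still at 15 after a year of treatment both qualify. A single score at entry does not tell them apart.

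Randomization would balance this on average, but there is none, and no matching or consecutive-sampling rule takes its place. The groups also enter by different routes: trained teams begin modBA with clinic patients, while the comparators are patients not yet receiving it. If the mix of early and late patients differs, the ordinary course of early treatment becomes part of the estimated modBA effect. At stake is the effect size that the pilot reports to inform a larger trial.

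**Working it through.** **1. The plan's own figure.** Section 1.5 gives 10 patients per team for 40 modBA patients, which implies 40 / 10 = 4 teams. Adding 40 usual-care patients gives 80. No alpha, power, SD or target difference is stated, so 80 can be reproduced only as this sum.

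**2. What 40 per group can show.** At two-sided 0.05 and 80% power, the detectable d is (1.960 + 0.842) x sqrt(2/40) = 0.63. Power at d = 0.5 is 61%. The 95% half-width on d is about 1.96 x sqrt(2/40) = 0.44.

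**3. Bias from an unequal mix.** None of the following values is in the documents. Assume new starters fall 5 PHQ-9 points over the observation period, long-treated patients fall 1.5, the SD of change is 5, and modBA has no effect.

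Spurious difference = (share of new starters in modBA - share in usual care) x (5 - 1.5).

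| New starters, modBA vs usual care | Calculation | Points | d | Rejection rate, 40 per group |
|---|---|---|---|---|
| equal shares | 0 x 3.5 | 0 | 0 | 5% |
| 60% vs 30% | 0.3 x 3.5 | 1.05 | 0.21 | 16% |
| 80% vs 20% | 0.6 x 3.5 | 2.10 | 0.42 | 47% |
| 30% vs 60% | -0.3 x 3.5 | -1.05 | -0.21 | 16% |
| 20% vs 80% | -0.6 x 3.5 | -2.10 | -0.42 | 47% |

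The rejection rates use the normal approximation with standard error 5 x sqrt(2/40) = 1.118. For 1.05 points the standardized shift is 1.05 / 1.118 = 0.94.

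**4. A second set of assumptions.** Let mean improvement after t weeks in treatment be D(1 - exp(-t/tau)) in both groups, with change taken over 12 weeks, D from 4 to 8 points and tau 6 or 10 weeks. For D = 6 and tau = 10, a group indexed at week 0 improves 6(1 - e^-1.2) = 4.19. A group indexed at week 8 improves 6(e^-0.8 - e^-2.0) = 1.88. The difference is 2.31 points.

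Over the whole grid (d at SD 5):
- week 0 vs week 8: 1.5 to 5.1 points (d 0.31 to 1.02)
- week 4 vs week 12: 1.0 to 2.6 points
- week 8 vs week 12: 0.4 to 0.9 points
- equal weeks: 0

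The sign reverses if the modBA group is further along. These cases move an entire group, so they are more extreme than step 3.

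**5. The baseline texts side by side.** The attached plan takes patient data before treatment starts and after it ends. Section 5.1 takes patients already in care and uses scores the clinic has recorded. The two agree only if the treatment meant is one the patient has not yet begun, and neither text says so.

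**The case against.** **Pre-treatment scores.** A reader might infer that no pre-treatment baseline exists. The documents do not support that. Historic PHQ and GAD scores are collected for every patient in both groups and may include values from before treatment. What is missing is a rule for which score is the baseline.

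**Stage of treatment.** A reader might also infer that patients enter at any stage of depression treatment. That rests only on the absence of a restriction. BVHC is a health center, and receiving care there need not mean being in therapy. For the same reason, collection before treatment initiation is not shown to be impossible; it is unreconciled with section 5.1.

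**Direction.** It is tempting to suppose that new referrals go to modBA and the existing caseload to usual care. No text says this; both groups are described as already receiving care. An imbalance is possible, not demonstrated, and could run either way.

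**Randomization.** The attached plan says "Therapists will be randomized to either modified BA, and will use their assigned intervention with 5 patients". That sentence names one arm only and conflicts with section 1.5 and with the attached plan's own Specific Aims, both of which call the trial non-randomized.

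**Pilot status.** The analysis is declared mainly descriptive, and nothing says the H2 effect size will set the size of a later trial. This limits the weight of the point. It does not remove it: effect sizes are a named output, H2 claims greater effectiveness, and confounding distorts a descriptive Cohen's d as much as a p-value.

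**Conclusion.** The point holds as a gap in design and analysis. The comparison is non-randomized, entry is unrestricted on time in treatment, no common index date or baseline score is set, and the planned test is unadjusted although the relevant variable is extracted.

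The conclusion is conditional: if stage of treatment differs between the groups, the H2 change estimates are biased. Under the assumptions in step 3, imbalances of 30 to 60 percentage points move the PHQ-9 difference by 1.05 to 2.1 points (d 0.21 to 0.42) towards or against modBA, and balance gives no bias. The upper value is about two thirds of the detectable d of 0.63. The documents supply neither the response values nor evidence of an imbalance, and no figure was derived for GAD-7. The change should be made before usual-care charts are drawn, but it does not put the pilot's feasibility aims in doubt.

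**What to change.** 1. Define one index visit for both groups: a visit with PHQ-9 10-20 within the same calendar window. Take the baseline PHQ-9 and GAD-7 there, and state the interval from that visit at which the follow-up score is read.
2. Where enough charts exist, draw usual-care patients to resemble the modBA patients on time in treatment at the index visit. All teams in the clinic are assigned to modBA, so the supply of concurrent usual-care charts should be checked first.
3. Report time in treatment by group.
4. For H2, replace the unadjusted t-test with a regression of the follow-up score on group, index score and time in treatment. Give the adjusted effect size with its confidence interval.
5. Reconcile the attached plan's timing of patient data collection, and its sentence on randomizing therapists, with sections 1.5 and 5.1.

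Effect sizes within strata of time in treatment are not a good substitute. Three even strata leave about 13 patients per group in each, and a 95% half-width on d of about 1.96 x sqrt(2/13) = 0.77.

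The cost is protocol wording, a sorting step when BVHC draws the sample, one or two degrees of freedom, and some usual-care charts passed over. No new data are needed. Adjustment handles only the stage of treatment that is measured; other differences between non-randomized groups remain and should be acknowledged.

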We will iteratively improve designs through usability testing with the clinicians and care managers. For example, if the *Discover* phase finds that the BA process needs to include no more than 3 steps, we may take the following steps:

1. The design team will create (for example) 3 different ways a BA component (such as activity charting) could be condensed, modified, or distributed differently in a workflow. These different processes will be depicted in electronic story boards.
2. The story boards will be shown to the clinicians with accompanying intervention materials (manuals, etc.). During the presentation, clinicians will be asked for their assessment of perceived usability (ease of learning, potential for use in clinic, perceived burden, and acceptability) for each iteration. These assessments will be both quantitative (System Usability Scale) and qualitative (Think Aloud). Quantitative data will be stored in the REDCap database, as will audio recordings of the Think Aloud Assessment.
3. Designers will then create a new version of the modification using information from all three storyboard assessments. The next version will be assessed using the processes described in step 2. This will continue until we reach a SUS scale score of .80. A final prototype will undergo initial feasibility evaluation in pilot field deployments with each clinician using the prototype with one depressed patient, with a PHQ-9 score between 10-20 (recruited from their WPRN clinic). Once we have completed the redesign of the EBPI so that it (1) meets needs of its clinicians and patients (i.e., is useful), and (2) is easy to use and understand (i.e., is usable), we will move to the *Test* phase (Phase 3) of this study.

Phase 3 Testing

We will conduct a pilot study comparing the modified EBPI to usual care at Bighorn Valley Health Center (BVHC). The EBPI itself (Behavioral Activation) will not change for the patients, but rather we will modify how Therapists and Care Managers at BVHC are sharing the tasks involved in Behavioral Activation. The modifications will also help guide Therapists and Care Managers as they decide how and

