when to use BA in specific clinical situations. The Therapists and Care Managers of some clinics in the BVHC network have already implemented this modified approach, and the goal is to have all clinics in the network learn and use the model. The Therapists and Care Managers will receive additional training and guidance from the study team to achieve this modification, but the patients' clinical care visits will not change. During the additional training, UW and Stanford study staff members will provide consultation on BVHC patient cases in order to provide support for any cases where BVHC clinicians are having difficulty using BA. During these discussions, no staff from the UW or Stanford team will ever know any identifiable information about the patients. However, both UW and Stanford staff members will have access to clinician participants' identifiable information from training/support activities with the clinicians. We will use pre-existing clinic measures to collect patient outcome data for patients whose providers are using the modified BA model. We will also collect patient outcomes using the same pre-existing clinic measures for patients whose providers are providing usual care. We will then compare outcome data for each type of care. A total of 11 clinicians and 80 patients will be recruited for Phase 3.

Clinician Procedures:

Clinician training in BA. UW team staff will train clinicians in modified Behavioral Activation elements per the protocol used by the AIMS Center, which includes training in basic brief treatment skills, therapeutic elements of the intervention and therapy process. The training will also include modifications developed via clinician/research staff co-design in Phase 2.

Note: These modifications will be developed in Phase 2, and new materials will be submitted to the IRB prior to beginning Phase 3.

Training will be followed by simulated case training. Once clinicians finish the training and begin using the modified BA with patients, we will use a self-report checklist and open-ended questions regarding the use of modified BA to measure clinicians' adherence to the model.

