a. Are there any procedures for which you will not obtain consent?

- No
- Yes → If yes, use the table below to identify the procedures for which you will not obtain consent. “All” is an acceptable answer for some studies.

Be sure to consider all research procedures and plans, including future contact, and sharing/banking of data and specimens for future work.

Group ¹	Describe the procedures or data/specimen collection (if any) for which there will be NO consent process	Reason why you will not obtain consent	Will you provide subjects with info about the research after they finish?	
			YES	NO
Patients	We will not consent patients for collection of data from their EHR (PHQ-9, GAD-7, demographics, process measures). We also will not consent patients for clinical care sessions they will complete after their therapists start receiving coaching on the Phase 3 research intervention.	Obtaining consent would likely cause confusion and provide no useful information to the patients because the research will not affect the basic therapies chosen or the structures of their clinical visits. In addition, some clinics have already implemented this approach outside of the research study, so patients are already receiving this model of care		

as part of their usual care prior to the research study.

	
	
	
	

Table footnotes

1. If your answer is the same for all groups you can collapse your answer across the groups and/or procedures.

b. Describe the consent process, if you will obtain consent for any or all procedures, for any or all groups. Address groups and procedures separately if the consent processes are different.

Be sure to include:

- The location/setting where consent will be obtained
- Who will obtain consent (refer to positions, roles, or titles, not names).
- Whether/how you will provide an opportunity for questions
- How you will provide an adequate opportunity for the subjects to consider all options

Clinician Participant Consent – Phases 1-3

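### Only the usual-care arm must be new to modified BA; the modified-BA arm can include patients already exposed to it, and no baseline or index date is defined

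*Combined protocol and SAP*

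**What the plan says.** All references are to the combined protocol and SAP.

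- **Modified-BA arm** (section 5.1, Patient Procedures): "Up to 40 patients who are already receiving care at BVHC will receive care via the BA task-sharing model". Eligibility rests on age 18 or older and on being a patient "who score between 10 and 20 on the PHQ-9".
- **Usual-care arm** (the next bullet): also up to 40 patients in care at BVHC, with an added condition, "but not yet receiving care via the modified BA model".
- **Exclusions** (section 2.2): suicidal intent or plan, and "history or presence of psychiatric diagnoses other than unipolar, non-psychotic major depression or generalized anxiety disorder will be excluded". Earlier modified BA is not mentioned.
- **Use of the model before the study:** section 5.1, Phase 3 Testing, states "The Therapists and Care Managers of some clinics in the BVHC network have already implemented this modified approach". Section 8.2.a uses the same fact to justify not seeking consent: "some clinics have already implemented this approach outside of the research study, so patients are already receiving this model of care".
- **Phase 2 deployment** (section 5.1, User Testing, step 3): the final prototype is tried with "each clinician using the prototype with one depressed patient, with a PHQ-9 score between 10-20".
- **Data** (section 5.1): weekly, historic and 3-month PHQ and GAD scores from the health record. No index date is named, and no score is designated as the qualifying or baseline value.
- **Hypothesis and analysis:** H2 in section 1.5 concerns change over time in PHQ-9 and GAD-7. The Data analysis paragraph of the appended research plan gives a t-test and Cohen's d without saying whether change or end scores are compared.

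**The concern.** Prior exposure to the model was thought relevant enough to write into one arm's entry rule but not the other's. As written, a patient who has had some weeks of modified BA and still scores 12 qualifies for the modified-BA arm, and that 12 can serve as the starting score. A patient who had the same weeks of modified BA and fell below 10 does not qualify. Controls cannot have had current exposure to the model.

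H2 depends on where the clock starts. If some modified-BA patients start part-way through the intervention and controls do not, the difference in change mixes two time origins. Aim 3 exists to inform a larger trial, and Cohen's d is the summary it would hand on. What is at stake is whether that figure can be interpreted.

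**Working it through.** The plan states no figure on this point, and it gives no alpha, power or standard deviation, so there is no calculation of its own to reproduce. The arm sizes agree: 40 + 40 = 80.

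**Step 1. Can an exposed patient enter the modified-BA arm?** The conditions are care at BVHC, age 18 or older, PHQ-9 of 10 to 20, and the two exclusions. None refers to earlier use of the model, so entry is permitted.

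**Step 2. Are there such patients?** There are two possible sources.
- *Clinics already using the model.* Sections 5.1 and 8.2.a say these exist. Neither gives a number, and neither says that their patients will fill the arm.
- *Phase 2 prototype patients.* Sections 2.1 and 2.7 allow up to 15 Phase 1 and 2 staff at the partnering centre. At one patient each, the arithmetic ceiling is 15/40 = 37.5% of the arm. Section 4.2 recruits Phase 3 clinicians from among Phase 2 participants, so the same patients may still be under their care.

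The Phase 2 text is not consistent. The User Testing paragraph says patients are not participants in that phase. Step 3 of the same subsection then has one patient recruited per clinician, and section 2.2 labels its patient criteria as covering Phases 2 and 3.

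**Step 3. Illustration of size.** Three quantities are assumed, because the documents do not give them:
- d = 0.50, the true standardised difference in change;
- f, the share of the modified-BA arm already exposed;
- g, the fraction of the model-specific benefit gained before the recorded baseline.

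For an analysis of change, d_observed = d × (1 − f × g).

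| f | g = 0.5 | g = 1 |
|---|---|---|
| 10% | 0.50 × 0.95 = 0.475 | 0.50 × 0.90 = 0.45 |
| 27.5% (11/40) | 0.50 × 0.8625 = 0.43 | 0.50 × 0.725 = 0.36 |
| 37.5% (15/40) | 0.50 × 0.8125 = 0.41 | 0.50 × 0.625 = 0.31 |

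The 27.5% row supposes that all 11 Phase 3 clinicians (sections 2.1, 4.1 and 5.1; the table in section 2.7 says 13) each bring one prototype patient. Clinics already using the model could add to f by an unknown amount.

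**Step 4. Does the formula apply?** Only if change scores are tested. If end scores are tested, benefit gained before baseline still counts at the end, and this dilution does not follow.

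**The case against.** The strongest reply is that the plan implies patients new to the model. Section 5.1 has clinicians begin using it after training, and the modified-BA bullet is in the future tense. The research plan's Patient data collection paragraph says data are collected before treatment starts and again after it ends. Together these suggest that many modified-BA patients would be switching to the model for the first time.

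That stands as a likelihood, but neither statement is an entry rule. The research-plan paragraph describes consented, paid assessments through a data portal, whereas sections 4, 5 and 8 describe unconsented extraction from the health record. It also does not say what the start of treatment means for someone already in care.

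A reader might go further and infer that the effect is biased downward, to about 0.31. The documents do not support that:
- The choice between change and end scores is not stated.
- The PHQ-9 window applies to both arms, and both are already in care, so losing early responders to existing care affects controls too.
- g = 1 sits badly with the floor of 10, which tends to leave partial responders.
- The 15 includes care managers and support staff, while patients are counted per team (40/10 = 4 teams), and the ceiling needs every prototype patient to re-enter.

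It is also fair that Aim 3 is a descriptive pilot, and that the historic scores and time in treatment already collected might allow an earlier baseline. No rule requires one, however, and a date of first contact with the model is not among the listed variables.

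**Conclusion.** The point holds as a gap in the entry rule and the time origin. The documents allow previously exposed patients into the modified-BA arm, exclude current users of the model from the control arm, and name no baseline score. On-treatment baselines are possible, not certain, and their number cannot be worked out from the documents.

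The consequence is a comparison that is hard to interpret. Its direction is uncertain: an analysis of change would tend to be diluted, and an analysis of end scores need not be. The range from 0.475 down to 0.31 is illustrative. It rests on an assumed d of 0.50, assumed f and g, and a test on change; 0.31 is the extreme corner for the Phase 2 route and not an expected value. Because the study team receives de-identified data (section 5.5), exposure that is not recorded at extraction may be impossible to recover later.

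**What to change.** 1. In sections 2.2 and 5.1, apply one rule to both arms: no contact with modified BA, task-sharing or the Phase 2 prototype before the index date.
2. For modified-BA patients, define the qualifying and baseline PHQ-9 and GAD-7 as the last scores before first contact with the model. Define a matching index date for controls.
3. Have the site add a first-contact date and a Phase 2 prototype flag to the de-identified extract. Phase 2 clinicians may have to supply the flag, since that phase is said to need no patient data.
4. If previously exposed patients are kept, report them separately.
5. Reconcile the research plan's statement on data-collection timing with the record-based procedures in section 5.1, and reconcile the two Phase 2 statements about patients. State whether change or end scores are tested.

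The cost is protocol wording, an added record field with its flag, and a check by the site champion. The downside is a somewhat smaller pool for the 40 modified-BA places.
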